9.6. Randomization

For randomization procedures, see Section 6.6.

9.7. Pharmacokinetics, Pharmacogenomics, Exploratory Biomarkers, and Anti-drug Antibodies

Blood and NP swab samples for pharmacokinetic analysis, pharmacogenomics, exploratory biomarkers, and anti-drug antibodies will be collected as indicated in the Schedule of Events (Table 1). Refer to the laboratory manual for instructions on collection of these samples for analysis.

Refer to the laboratory manual for instructions on collection of samples from nasopharyngeal swab for exploratory CD388 assays.

9.8. Reactogenicity/Injection Site Inspection

At indicated visits, inspection of administration site and surrounding area will be performed twice daily, with any abnormal findings reported as AEs. Reactions will be rated according to Table 5.

Table 5: Injection Site Evaluation

Local Reaction	Mild (Grade 1)	Moderate (Grade 2)	Severe (Grade 3)	Potentially Life Threatening (Grade 4)
Pain	Does not interfere with activity	Repeated use of non-narcotic pain reliever >24 hours or interferes with activity	Any use of narcotic pain reliever or prevents daily activity	Emergency room (ER) visit or hospitalization
Tenderness	Mild discomfort to touch	Discomfort with movement	Significant discomfort at rest	ER visit or hospitalization
Erythema/Redness ^a	2.5–5 cm	5.1–10 cm	>10 cm	Necrosis or exfoliative dermatitis
Induration/Swelling b	2.5–5 cm and does not interfere with activity	5.1–10 cm or interferes with activity	>10 cm or prevents daily activity	Necrosis

a. In addition to grading the measured local reaction at the greatest single diameter, the measurement should be recorded as a continuous variable.

9.9. Adverse Events

Information on AEs (event term, start and stop dates, severity, relationship to blinded study drug) will be collected from the time of signing the informed consent form (ICF) until the final study visit after the dose of study drug. See Section 11 for additional information.

9.10. Prior and Concomitant Medications and Concomitant Procedures

Prior and concomitant medication usage will be recorded from 28 days prior to CD388 Injection/placebo administration until the final study visit. See Section 8.5 for permitted concomitant medications.

Concomitant procedures to treat an AE will be recorded from the time of CD388 Injection/placebo administration until the final study visit.

b. Induration/swelling should be evaluated and graded using the functional scale as well as the actual measurement. Source: (FDA 2007).

10. ASSESSMENT OF EFFICACY

Not applicable; this study has no efficacy endpoints.

11. ASSESSMENT OF SAFETY

11.1. Safety Parameters

Safety and tolerability will be assessed by monitoring AEs (including systemic reactogenicity/injection site reactions, hypersensitivity reactions, and AESIs), vital signs, 12-lead ECGs, clinical laboratory results (hematology, coagulation, serum chemistry, urinalysis), and concomitant medication usage throughout the study.

11.2. Adverse Events

Adverse events will be collected for all subjects from the time of signing the ICF through the final study visit. The Investigator will assess all AEs and SAEs and will record the following information on the appropriate eCRF page:

- Date of onset
- Resolution status, and date of resolution or stabilization if achieved
- Seriousness
- Severity
- Causal relationship to study drug
- Action taken with study medication

Medically indicated laboratory tests (emergency or unscheduled tests) should be conducted at the local laboratory. The Investigator should employ best medical judgment in determining how to manage AEs and SAEs. Any questions regarding AE or SAE management should be directed to the Medical Monitor.

The Sponsor is responsible for:

- Confirming the seriousness assessment of all reported AEs and SAEs
- Confirming the causal relationship between reported AEs/SAEs and the investigational product
- Assessment of SAEs for expectedness

The Sponsor will continuously assess the safety of the investigational product throughout the study.

11.3. Adverse Event Reporting

11.3.1. Notification of Serious Adverse Events

The Sponsor has requirements for expedited reporting of SAEs meeting specific criteria to worldwide regulatory authorities in accordance with ICH guidelines and local regulatory requirements. Therefore, the Investigator must notify the Sponsor immediately regarding any SAE that occurs after informed consent via transmission of a Serious Adverse Event Report (SAER) by the study site to the safety vendor by email within 24 hours of awareness that an SAE

has occurred, with a copy to the Medical Monitor. Contact details will be provided to the site(s). An optional initial report can be made via telephone, but a completed SAER must still be emailed within 24 hours of the site's knowledge of the event.

The Investigational site will be provided with SAER forms wherein the following information is requested:

- Subject identification, Investigator name, and site number
- SAE information: event term, onset date, severity, and causal relationship
- The outcomes attributable to the event (e.g., death, a life-threatening AE, inpatient hospitalization, prolongation of existing hospitalization, a persistent or significant disability or incapacity, or other important medical event[s]; refer to Section 11.4.4)
- A summary of relevant test results, pertinent laboratory data, and any other relevant medical history
- The date of study drug administration (NOTE: as this is a double-blind study, SAERs should not indicate specific study drug assignments)

Supplemental information may be requested, including the following: hospital records, laboratory results, radiology reports, progress notes, admission and emergency room notes, holding and observation notes, discharge summaries, autopsy reports, and death certificates.

Relevant eCRF pages can be appended to communicate information relevant to the SAE, including study drug administration details, medical history, concomitant medications, relevant laboratory test results, and subject outcome information. The SAER should be emailed within 24 hours with as much of the above information as available at the time. The following minimum information is required for reporting an SAE: subject identification, Investigator contact information, an AE with a serious outcome, and the Investigator's assessment of causal relationship to study drug. Serious adverse events are to be reported immediately and under no circumstance should this reporting time exceed 24 hours following knowledge of the SAE. Supplemental information may be transmitted using a follow-up report and should not delay the initial report. The Sponsor may contact the investigational site to solicit additional information or follow up on the event.

The Investigator must take all therapeutic measures necessary for resolution of the SAE. Any medications or procedures necessary for treatment of the SAE must be recorded on the appropriate pages of the subject's eCRF.

If the Investigator becomes aware of any SAEs that occur after the study period that are believed to be causally related to use of the investigational product, they should notify the Sponsor immediately.

The Sponsor will report all suspected unexpected serious adverse reactions (SUSARs) within the required regulatory timeframes to all applicable regulatory authorities and to Investigators as required.

All SAEs that do not meet expedited reporting requirements will be summarized in the Development Safety Update Report (DSUR) and reported annually by the Sponsor as required.

11.3.2. Notification of Emerging Safety Issues

Additionally, the Investigator should alert the Sponsor immediately (under no circumstance should this reporting time exceed 24 hours) by contacting the Medical Monitor of any new findings that necessitate the implementation of urgent safety measures to protect subjects against any immediate hazard. If time permits, the Investigator should contact the Sponsor to discuss the hazard and any actions taken or to be taken prior to implementation.

The Sponsor is responsible for informing other investigators who may need to implement the same procedures and for alerting the Competent Authorities and Ethics Committees of the new findings and measures taken in accordance with local regulations within the required timeframes.

11.4. Definitions

11.4.1. Adverse Event

An AE means any untoward medical occurrence associated with the use of a drug or study procedure in humans, whether or not considered drug-related. An AE can be any unfavorable and unintended sign (e.g., a clinically significant abnormal laboratory finding), symptom, or disease temporally associated with the use of a drug and does not imply any judgment about causality. An AE can arise with any use of the drug (e.g., off-label use, use in combination with another drug) and with any route of administration, formulation, or dose, including an overdose.

Laboratory abnormalities should not be recorded as AEs or SAEs unless they are associated with clinical signs or symptoms, or require medical intervention. However, each laboratory abnormality (e.g., clinically significant changes detected on hematology, coagulation, chemistry, urinalysis) independent from any underlying medical condition that requires medical or surgical intervention, or that leads to interruption of study drug or discontinuation, must be recorded as an AE, or SAE if applicable. If the laboratory abnormality is part of a clinical condition or syndrome, it should be recorded as the syndrome or diagnosis rather than as the individual laboratory abnormality. In addition, laboratory abnormalities or other abnormal test assessments (e.g., ECGs) that are associated with signs or symptoms must be recorded as AEs or SAEs if they meet the definition of an AE or SAE as described in this section and in Section 11.4.4, respectively.

11.4.2. Suspected Adverse Reaction

A suspected adverse reaction is any AE for which there is a reasonable possibility that the drug caused the AE. For the purposes of Investigational New Drug (IND) safety reporting, "reasonable possibility" means there is evidence to suggest a causal relationship between the drug and the AE. "Suspected adverse reaction" implies a lesser degree of certainty about causality than "adverse reaction", which means any AE caused by a drug.

11.4.3. Life-Threatening AE or Life-Threatening Suspected Adverse Reaction

An AE or suspected adverse reaction is considered "life threatening" if, in the view of either the Investigator or Sponsor, its occurrence places the subject at immediate risk of death. It does not include an AE or suspected adverse reaction that, had it occurred in a more severe form, might have caused death.

11.4.4. Serious Adverse Event or Serious Suspected Adverse Reaction

An AE or suspected adverse reaction is considered "serious" if, in the view of either the Investigator or Sponsor, it results in any of the following outcomes:

- Death
- A life-threatening AE see definition above
- Inpatient hospitalization or prolongation of existing hospitalization
- A persistent or significant incapacity or substantial disruption of the ability to conduct normal life functions
- A congenital anomaly/birth defect in the offspring of a subject who received study drug
- Is a suspected transmission of any infectious agent via a medicinal product
- Important medical events that may not result in death, be life-threatening, or require hospitalization may be considered serious when, based upon appropriate medical judgment, they may jeopardize the patient or subject and may require medical or surgical intervention to prevent one of the outcomes listed in this definition

11.4.5. Unexpected AE or Unexpected Suspected Adverse Reaction

An AE or suspected adverse reaction is considered "unexpected":

• If it is not listed in the Investigator's Brochure or is not listed at the nature, severity, frequency, or outcome that has been observed

For example, under this definition, hepatic necrosis would be unexpected (by virtue of greater severity) if the Investigator's Brochure referred only to elevated hepatic enzymes or hepatitis. Similarly, cerebral thromboembolism and cerebral vasculitis would be unexpected (by virtue of greater specificity) if the Investigator's Brochure listed only cerebral vascular accidents.

"Unexpected", as used in this definition, also refers to AEs or suspected adverse reactions that are mentioned in the Investigator's Brochure as occurring with a class of drugs or as anticipated from the pharmacological properties of the drug but are not specifically mentioned as occurring with the particular drug under investigation.

11.4.6. Adverse Events of Special Interest

Adverse events of special interest (AESIs) include anaphylaxis (refer to Appendix 3 for diagnostic criteria and management).

11.4.7. Emerging Safety Issue

Any new safety information that may lead to a reassessment of the risk/benefit balance of the investigational product and/or impact subjects' health. Examples include:

• Any new safety issue relating to the conduct of the clinical trial that may impact the safety of the trial subjects such as significant safety results from a recently completed non-clinical study or early termination or temporary suspension of a trial for safety reasons that is conducted on the same investigational product

• Recommendations from a Data Review Committee that may affect the safety of trial subjects

11.4.8. Urgent Safety Measure

An urgent safety measure (USM) is a procedure not defined by the protocol that can be put in place immediately, without prior authorization from Ethics Committees or Regulatory Authorities, to protect study subjects from any immediate hazard to their health and safety.

11.5. Adverse Event Classification

11.5.1. Relationship to Study Drug

The Investigator's assessment of causality must be provided for all AEs (serious and nonserious; Table 6). An Investigator's causality assessment is the determination of whether there exists a reasonable possibility that the study drug caused or contributed to an AE.

These criteria, in addition to good clinical judgment, should be used as a guide for determining the causal assessment. If the event is thought to be unrelated to study drug administration, an alternative explanation should be provided.

Table 6: Table Guidelines for Assessing Relationship of Event to Study Drug

Unrelated	There is little or no chance that the study drug caused the adverse event (AE); other conditions, including concurrent illnesses, progression or expression of the disease state, or a reaction to a concomitant medication best explain the event.
Related	The association of the AE with the study drug is unknown; however, the AE is not clearly due to another condition, or a reasonable temporal association exists between the AE and study drug administration and, based on the Investigator's clinical experience, the association of the AE with the study drug seems likely.

11.5.2. Severity

For injection site reactions, the Investigator will use the grading scale in Table 5. To describe the intensity of all other AEs following general categorical descriptors outlined in the DAIDS table for Grading the Severity of Adult and Pediatric Adverse Events (DAIDS 2017), the grading scale in Table 7 will be used.

Table 7: Guidelines for Severity Assessments

Grade 1 Mild	Mild symptoms causing no or minimal interference with usual social and functional activities with intervention not indicated
Grade 2 Moderate	Moderate symptoms causing greater than minimal interference with usual social and functional activities with intervention indicated
Grade 3 Severe	Severe symptoms causing inability to perform usual social and functional activities with intervention or hospitalization indicated
Grade 4 Potentially Life Threatening	Potentially life-threatening symptoms causing inability to perform basic self-care functions with intervention indicated to prevent permanent impairment, persistent disability, or death
Grade 5 Death	Fatal

Refer to the DAIDS table for Grading the Severity of Adult and Pediatric Adverse Events for details regarding event grading.

11.5.3. Serious Adverse Event

Any adverse experience occurring at any dose of study medication that occurs from the time of informed consent through the final study visit, are considered serious if they result in any of the outcomes listed in Section 11.4.4.

Hospitalization for a planned or elective procedure or surgery for a pre-existing condition that has not worsened is not considered an SAE.

11.6. Adverse Event Follow Up

All unresolved SAEs and study drug-related AEs will be followed by the study staff until resolution or deemed stable, regardless of severity.

11.7. Adverse Event Management

The Investigator should employ best medical judgement in determining how to manage AEs. Any questions regarding AE management should be directed to the Medical Monitor.

11.8. Risks for Women of Childbearing Potential or During Pregnancy

The risks of CD388 Injection in pregnant or lactating/nursing women are unknown. Pregnant or nursing female subjects are excluded from this study.

Subjects must be instructed to inform the Investigator immediately if they or their partner becomes pregnant during the study. In the case of a partner pregnancy, partner informed consent must be obtained prior to collecting information related to the pregnancy and to allow the Investigator to follow them for the outcome of the pregnancy. In the event of a confirmed pregnancy, the following actions should be taken:

- The pregnancy should be reported to the Sponsor within 24 hours of the subject notifying the Investigator using the applicable Pregnancy Report Form.
- The Investigator should counsel female subjects regarding the possible effects of CD388 Injection exposure on the fetus and the need to inform the study site of the outcome of the pregnancy.
- The subject or subject's partner, if consented, should be monitored until the postnatal day 28 or until termination of the pregnancy. The outcome should be reported using the Pregnancy Outcome or Abnormal Pregnancy Outcome form.

Pregnancy is not an AE, in and of itself. However, any pregnancy complication or elective termination of a pregnancy for medical reasons will be recorded as an AE or SAE. A spontaneous abortion is always considered an SAE and will be reported as described in the AE and SAE sections. Furthermore, any SAE occurring as an adverse pregnancy outcome post-study must be reported to the Medical Monitor.

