1.1. Schedule of Events

Table 1: Schedule of Events

	Screening		Clinica	al Resea	Clinical Research Unit (CRU) Inpatient Stay	(CRU) I	npatient	Stay			Outpa	Outpatient CRU Visits	tU Visit	20
Day (Window)	-28 to -2	-1	1	2	3–6	L	6	11	14	30 (±3)	45 (±3)	(5±)	90 (±7)	120/165 a (±14)
Informed consent	X													
Inclusion/Exclusion criteria	X	X												
Medical history/demographics	X													
Complete physical with vital signs (BP, RR, HR, oral temperature, height, weight, BMI)	X													
Targeted physical with vital signs (BP, RR, HR, oral temperature, weight ^b)		×	×°	×	X	X			×	X	X	×	×	×
Safety ECG ^d	X	X	X			X			×	X				X
Laboratory evaluations (CBC with platelets, coagulation, serum chemistry, lipids, urinalysis)	X	X		X	X e	X			X	X	X	X	X	×
Virology screening (HBV, HCV, HIV)	X													
Virology screening (SARS-CoV-2)		×												
Serum/urine pregnancy test f	X	X								X		×	X	X
FSH (if applicable to confirm postmenopausal status)	X													
Drug/alcohol screen 8	X	X												
Randomization			X											
Dosing of study drug			X											
Reactogenicity/injection site inspection h			X	X	X									
PK sample collection i			X	X	X	X	X	X	X	X	X	X	X	X
Pharmacogenomics blood sample ^j			predose											
Exploratory biomarker samples			predose		X e									
Anti-drug antibodies			predose						X	X	X	X	X	X
Nasopharyngeal swab collection ^k			predose	X	X	X	X	X	X	X				
Assess and record AEs ¹	→													↑
Concomitant medications/procedures review m	\													↑

[figure not shown]
research unit; DAR = drug-antibody ratio; ECG = electrocardiogram; FSH = folliele-stimulating hormone; HBV = hepatitis B virus; HCV = hepatitis C virus; HIV = human Abbreviations: AEs = adverse events; BMI = body mass index; BP = blood pressure, CBC = complete blood count; COVID-19 = coronavirus disease 2019; CRU = clinical immunodeficiency virus; HR = heart rate; hr = hour; ICF = informed consent form; PK = pharmacokinetic; RR = respiration rate; SARS-CoV-2 = severe acute respiratory syndrome coronavirus 2.

Schedule of Events (continued)

- The timing of this visit is Day 120 for Cohort 1 and Day 165 for Cohorts 2 and 3. For subjects who discontinue study early, the Day 120/165 procedures should be performed.
- b. Weight should be measured at each of the outpatient visits (Days 30, 45, 60, 90, 120/165).

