- On Day 1, the targeted physical examination should be performed predose. Vital signs collection will occur predose, 6 hours postdose, and as clinically indicated, and will be measured with the subject in a seated position for at least 3 minutes prior to measurement. ပ
- A triplicate 12-lead ECG is to be performed at screening, at CRU check-in on Day -1, predose (immediately prior to study drug administration) and 6 hours postdose (±10 minutes) on Day 1, and as indicated in the schedule. Subjects are to be resting (at least 5 minutes) and semi-recumbent when ECG is being conducted. d.
- Laboratory evaluations (including exploratory biomarker samples) need to be performed once during the Day 3-6 interval on Day 4. e.
- A sensitive serum pregnancy test (\(\beta\)-human chorionic gonadotropin) is required at screening and Day 120/165 for females of childbearing potential. Urine pregnancy test may be performed at all other time points. £.
- Drug and alcohol screen is to be performed during the outpatient visits if vital signs are abnormal (see Appendix 2). ьio
- and once approximately 8-12 hours postdose, then twice daily on other indicated study days at least 6 hours apart), with any abnormal findings reported as At indicated visits, inspection of administration site and surrounding area will be performed twice daily (once between approximately 2-4 hours postdose, AEs. Reactions will be rated according to the scale provided in Table 5. þ.
- Blood samples for PK analysis will be collected predose (-24 hour window); post-dose at 2, 4, and 12 hours (each ±10 minute window); 24 hours (±30 minute window); 48 hours (±1 hour window); 72, 96, 120 hours (each ±2 hour window); and in the morning on Days 7, 9, 11, 14. Postdose samples collected at outpatient CRU visits at Days 30, 45, 60, 90, and 120/165 have the same windows (i.e., in ±days) as the visits. . 🚅
- A mandatory pharmacogenomic (DNA) blood sample will be collected once, preferably on Day 1 (collection at another time point is allowed if necessary) to allow for pharmacogenomic research related to CD388. ..
- Nasopharyngeal swab samples will be collected predose on Day 1, and on Days 2, 5, 7, 9, 11, 14, and 30. 7
- Adverse events (including influenza-like illness which will be tested for both COVID-19 and flu) will be collected for all subjects from the time of signing the ICF through the final study visit.

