6.5. Expected Duration of Subject Participation

A single dose of study drug will be administered SQ on Day 1. Study participation will require up to 28 days for screening procedures, and approximately 120/165 days for dosing and follow-up (check-in to the CRU on Day -1; CRU inpatient stay for study drug administration, observation, and assessments and procedures for 15 days [Days -1 to Day 14]; and 5 CRU outpatient visits for additional assessments and procedures).

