7. SELECTION, DISCONTINUATION, AND WITHDRAWAL OF SUBJECTS

7.1. Subject Inclusion Criteria

Subjects must meet ALL the following inclusion criteria:

- 1. Must be of Japanese descent with Japanese parents and grandparents, as determined by subject's verbal report.
- 2. Willing and able to provide written informed consent.
- 3. Males and females 18 to 65 years of age, inclusive.
- 4. A female subject must meet one of the following criteria:
 - a. If of childbearing potential agrees to use a highly effective, preferably user-independent method of contraception (failure rate of <1% per year when used consistently and correctly) for at least 30 days prior to screening and agrees to remain on a highly effective method until 7 months after last dose of study medication. Examples of highly-effective methods of contraception are located in Appendix 1.
 - b. If a female of non-childbearing potential should be surgically sterile (i.e., has undergone complete hysterectomy, bilateral oophorectomy, or tubal ligation/occlusion without reversal surgery) or in a menopausal state (at least 1 year without menses), as confirmed by follicle-stimulating hormone (FSH) levels (≥40 mIU/mL).
- 5. A woman of childbearing potential must have a negative highly sensitive serum pregnancy test (β-human chorionic gonadotropin) at screening and a negative urine pregnancy test on Day -1 before the first dose of study drug.
- 6. A woman must agree not to donate eggs (ova, oocytes) for the purposes of assisted reproduction during the study and for a period of at least 7 months after study drug administration.
- 7. A male subject that engages in sexual activity that has the risk of pregnancy must agree to use a double barrier method (e.g., condom and spermicide) and agree not to donate sperm during the study and for at least 7 months after the last dose of the study medication.
- 8. Good health and without signs or symptoms of current illness.
- 9. Normal clinical examination, including:
 - a. No physical examination findings that an Investigator determines would interfere with interpretation of study results.
 - b. Screening ECG without clinically significant abnormalities (see Appendix 2).
 - c. Creatinine clearance (CrCL) ≥80 mL/min as calculated using the Cockcroft-Gault equation:

$$CrCL = \frac{(140 - age) \times (weight in kg)}{72 \times (serum creatinine in mg/dL)} \times (0.85 if female)$$

- d. Negative urine screen for drugs of abuse and alcohol at screening and Day -1.

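### Section 11.8 limits the subject's duty to report a pregnancy to the study period, leaving the last 49 to 94 days of the 7-month precaution window without a reporting instruction

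*Protocol*

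**What the plan says.** Section 11.8 states that the risks of CD388 in pregnancy are unknown and sets the subject's duty: "Subjects must be instructed to inform the Investigator immediately if they or their partner becomes pregnant during the study".

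The precautions in Section 7.1 run for a longer time:

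- Criterion 4a, for women of childbearing potential: the subject "agrees to remain on a highly effective method until 7 months after last dose of study medication".
- Criterion 6: no egg donation "during the study and for a period of at least 7 months after study drug administration".
- Criterion 7: men at risk of fathering a pregnancy use a double barrier method and "agree not to donate sperm during the study and for at least 7 months after the last dose of the study medication".

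The calendar comes from Sections 1.1 and 6.5. There is one dose, on Day 1, and participation takes "approximately 120/165 days for dosing and follow-up". For the final visit, "The timing of this visit is Day 120 for Cohort 1 and Day 165 for Cohorts 2 and 3", with a window of ±14 days. A serum pregnancy test "is required at screening and Day 120/165 for females of childbearing potential", and no test is scheduled after that.

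The site's duties in Section 11.8 begin "In the event of a confirmed pregnancy, the following actions should be taken" and carry no end date.

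**The concern.** The sponsor judged that conception should be avoided for 7 months after exposure. A contraceptive failure inside that window is therefore an event the sponsor would want to know about, yet the instruction to report it stops earlier. Criteria 6 and 7 add the 7 months to the study period; if the study period already reached that far, the addition would be redundant. Section 11.8 names only the study period.

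At stake is safety information on a drug whose pregnancy risk is unknown. After the final visit, an uncomplicated pregnancy or a non-serious complication in a subject or partner could go unreported simply because nobody asked for it. No objective, endpoint or analysis depends on this.

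**Working it through.** The protocol gives no figure to reproduce. The check is calendar arithmetic followed by a rough expected count.

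**1. Length of the precaution window.** 7 × 30.44 = 213 days after the Day 1 dose.

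**2. Time from dose to final visit.** Day 120 is 119 days after a Day 1 dose; Day 165 is 164 days after it.

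**3. Uncovered interval if the study ends at the subject's own final visit.**

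| Cohort | Nominal gap (days) | Across the ±14-day window (days) |
|---|---|---|
| 1 | 213 − 119 = 94 | 80 to 108 |
| 2 and 3 | 213 − 164 = 49 | 35 to 63 |

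Seven calendar months last 212 to 215 days depending on the start date. Allowing for that widens the ranges to 79–110 and 34–65 days. The gap is positive for every cohort at every permitted visit date.

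**4. Uncovered interval if the study ends at the last subject's last visit (Section 13.5).** Suppose the last-dosed subject is in Cohort 3. A subject dosed *d* days earlier is then covered to 164 + *d* days after dosing, so the gap is max(0, 49 − *d*). It is 49 days for the last-dosed subject at the nominal visit day and zero for anyone dosed at least 49 days earlier.

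**5. Other routes by which the site could learn of a conception after the final visit.**

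- Scheduled testing: the last test is at the final visit, and partners are not tested.
- Adverse event collection (Section 11.2): ends at the final visit.
- Post-study clauses: Section 11.3.1 covers serious events the Investigator hears of and believes drug-related. Section 11.8 covers serious adverse pregnancy outcomes. Neither tells the subject to report a pregnancy.

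**6. Expected number of events (reading in step 3).** There are 7 CD388 subjects in Cohort 1 and 14 in Cohorts 2 and 3. All 21 are counted as at risk, which overstates the time because sterile, postmenopausal and not-at-risk subjects are included. The rate is 1% per year, the ceiling in criterion 4a.

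| Final visit | Uncovered subject-days | Years | × 0.01 per year |
|---|---|---|---|
| Nominal | 7 × 94 + 14 × 49 = 1344 | 3.68 | 0.037 |
| +14 days | 7 × 80 + 14 × 35 = 1050 | 2.87 | 0.029 |
| −14 days | 7 × 108 + 14 × 63 = 1638 | 4.48 | 0.045 |

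That range reflects the visit date only. The protocol gives no failure rate for the men's double barrier method, so 1% is an assumption for them. The count is proportional to the rate: if every subject had ten times the ceiling, the nominal figure would be 3.68 × 0.10 = 0.37, still below one event.

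**The case against.** The strongest reply is that nothing here is contradictory. Contraception prevents exposure and Section 11.8 governs reporting, and the two periods need not end together. The outcomes that matter most are also covered. Pregnancies that begin in the study are followed to postnatal day 28 or termination. Spontaneous abortion is always serious (Section 11.8), as is a congenital anomaly in the offspring of a dosed subject (Section 11.4.4). Serious pregnancy outcomes after the study must be reported, and a site that learns of a later pregnancy can act because its duties have no end date. The consent form, the natural place for the instruction, was not available and may already cover the full 7 months.

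Much of this stands and sets the weight of the point. It does not close the gap. The post-study duties bind the site and work only if the site hears of the event, and the missing instruction is the one that would let it hear.

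Two narrower objections deserve an answer:

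- The wording of criteria 6 and 7 is not conclusive. The study period starts at screening, so naming it alongside the 7 months also adds pre-dose time. That is fair, but the gap follows from the visit schedule alone.
- Section 13.5 could be taken to stretch the study to the last subject's last visit. That definition is made for registries and end-of-trial notifications, a subject cannot know when another subject's last visit falls, and the last-dosed subject is left uncovered even so.

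**Conclusion.** The point holds as a minor design weakness with an inexpensive remedy. Section 11.8 fixes a notification period shorter than the protocol's own precaution window by about 94 days in Cohort 1 and 49 days in Cohorts 2 and 3. This takes the study to end at each subject's own final visit; on the trial-level reading the gap is at most 49 days at the nominal visit day and zero for many subjects. The expected number of affected pregnancies is about 0.04 under the stated assumptions of all 21 CD388 subjects at risk and 1% per year for both sexes. What could be lost is news of uncomplicated pregnancies and non-serious complications. No trial result is affected. Whether subjects are in practice left uninstructed depends on the consent form, which was not seen.

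**What to change.** In Section 11.8, change the end of the subject's notification period from the study alone to *during the study and until 7 months after study drug administration*. Check that the consent form gives subjects the same instruction. The contraception and donation rules stay as they are.

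The cost is one phrase, best carried in the next amendment because a protocol change needs Sponsor approval (Section 13.1) and goes to the IRB (Section 15.2), plus the consent-form check. No visit, test or scheduled contact is added. The one added burden is that the site would have to follow any pregnancy reported after the final visit to postnatal day 28 or termination, with partner consent where that applies.
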